10.4 Patient-reported measures

10.4.1 Frailty Assessment

For practices randomized to Arm 2, see Appendix III; For practices randomized to Arm 3, see Appendix X.

10.4.2 Functional Assessment (CHAMPS)

Physical function will be measured preoperatively and 8 weeks after surgery using the CHAMPS questionnaire in patients who consent for this portion of the study. CHAMPS includes 41 questions that ask the senior to estimate the time spent on a range of activities in the previous week. It has been validated as a measure of recovery of physical function after surgery and significantly correlates with SF-36 Physical Function, pain with movement, and 6 minute walking test distance.²⁶

10.4.3 EQ-5D-5L

EQ-5D-5L is a short, 6-question, instrument which assesses a patient's health state. The addition of the EQ-5D-5L will allow for computation and comparison of health utilities between arms.

11.0 END OF INTERVENTION

11.1 Duration of Intervention

Patient-level intervention will continue until surgery.

For practices randomized to the OPTI-Surg plus Coach arm, **site-level intervention** will continue until 24 weeks after site activation.

11.2 Follow-up

11.2.1 Duration of follow up

Patient level follow-up: Patients will be followed for surgical complications until 12 weeks after surgery.

Practice level follow-up: For practices selected to undergo site interviews, follow up will continue until 6-9 months after the last patient is registered at that practice.

11.2.2 Extraordinary Medical Circumstances

If, at any time the constraints of this protocol are detrimental to the patient's health and/or the patient no longer wishes to continue protocol therapy, protocol therapy shall be discontinued. In this event:

- Document the reason(s) for discontinuation of therapy on data forms.
- Follow the patient for protocol endpoints as required by the Study Calendar.

11.3 Managing ineligible patients and registered patients who never receive protocol intervention

Definition of ineligible patient

A study participant who is registered to the trial but does not meet all of the eligibility criteria is deemed to be ineligible.

Follow-up for ineligible patients who continue with protocol treatment

Patients who are deemed ineligible after registering may continue protocol treatment, provided the treating physician, study chair, and executive officer agree there are no safety concerns if the patient continues protocol treatment. All scans, tests, and data submission are to continue as if the patient were eligible. Notification of the local IRB may be necessary per local IRB policies.

Follow-up for patients who are registered, but who do not undergo surgery

For all study participants who are registered to the trial but who never receive study intervention (regardless of eligibility), baseline and off-treatment notice data submission are required. See the Data Submission Schedule accompanying the All Forms Packet.

12.0 STATISTICAL CONSIDERATIONS

12.1 Statistical design

This is a cluster randomized trial to evaluate the effectiveness of OPTI-Surg at the practice level. Practices will be randomized in a 1:1:1 fashion to the OPTI-Surg package intervention alone, OPTI-Surg with an implementation coach, or usual care. The comparison of coach versus no-coach arms will provide data on which practice change strategies are effective while ensuring that strategies are feasible and acceptable. Our design also includes direct measurement of practice culture and intervention roll-out through mixed methods (surveys, observation, and qualitative interviews). These mixed-methods data will identify barriers to implementation and acceptability, inform continuous improvement of the intervention, and provide insights into how to tailor the intervention to individual practice sites to ensure effective dissemination. The primary analysis will be conducted after the last enrolled patient has been followed for at least 12 weeks.

Interim analysis: Futility will be declared if the p-value is ≥ 0.323 based on a non-binding Pocock boundary with a Lan-DeMets spending function after half the consented patients have been observed at 8 weeks (i.e., completed the CHAMPS). We will also prospectively monitor enrollment (both number of practices and number of patients per practice) and modify the planned number of practices in order to lower the number of patients per practice if per-practice enrollment rates are slower than expected.

12.2 Endpoints

12.2.1 Primary endpoint: CHAMPS total score 8 weeks after surgery. Hypothesis: Among surgical practices that are randomized to OPTI-Surg (with or without a coach), patient-reported function will be higher as compared to the surgical practices randomized to usual care.

Secondary endpoints:

12.2.2 Postoperative complications (Clavien-Dindo grades I-V) within 12 weeks of surgery. Hypothesis: Among surgical practices that are randomized to OPTI-Surg (with or without

a coach), a lower proportion of patients will experience postoperative complications as compared to the surgical practices randomized to usual care.

12.2.3 Compliance with administration of the EFS. Hypothesis: Compliance with screening will be higher among surgical practices that are randomized to OPTI-Surg with a coach versus those without a coach.

Exploratory endpoints:

12.2.4 Postoperative mortality, hospital length of stay, discharge to a facility, and hospital readmission within 12 weeks of surgery.

12.2.5 Subsequent administration of interventions as a result of the EFS.

12.2.6 Barriers and facilitators to implementation through mixed-methods research.

12.3 Power and sample size

Target sample size of 15 patients (maximum 25) per each of 30 surgical practices (450 patients total) is based on achieving 90% power with a two sided alpha of 0.05 using a generalized linear mixed model (with Gaussian link function) with a random practice effect to account for clustering within practice to compare function at 8 weeks between the combined OPTI-Surg no-coach and coach arms versus usual care, adjusting for baseline function, with the following assumptions:

1. Among patients who are 70 years of age or older, 59% will be identified as frail with potential maximal benefit from OPTI-Surg screening (we assume partial effectiveness [33% of the full effect size] of OPTI-Surg screening in the remaining 41% of patients who are not found to be frail based on effectiveness of the Li (2013)²⁷ intervention in a non-screened population).
2. OPTI-Surg screening compliance will be 60% and 80% in the no-coach and coach arms.
3. Impact of OPTI-Surg within frail and screened patients (versus frail patients in the usual care arm) is based on a prior study of a similar intervention showing mean CHAMPS score (kcal) of 23 versus 8 at 8 weeks post-surgery.²⁷ The overall effect size, taking into account frailty rates and screening rates as described above, is a mean score (kcal) of 19.73 versus 12.10 at 8 weeks post-surgery for the combined OPTI-Surg no-coach/coach arms and usual care arm, respectively (standardized effect size of 0.42 [based on a CHAMPS standard deviation of 18.3] for the difference between arms). This explicitly takes into account the following mean CHAMPS scores in patients of this study:
 - a. Among frail patients in the OPTI-Surg arms who are screened, 8-week mean score=23.
 - b. Among frail patients in the OPTI-Surg arms who are not screened, 8-week mean score=8.
 - c. Among non-frail patients in the OPTI-Surg arms who are screened, 8-week mean score=23.
 - d. Among non-frail patients in the OPTI-Surg arms who are not screened, 8-week mean score=18.
 - e. Among frail patients in the usual care arm, 8-week mean score=8.
 - f. Among non-frail patients in the usual care arm, 8-week mean score=18.
4. Cluster effect will be 0.005.²⁸

5. Standard deviation of the CHAMPS score (kcal) is 18.3.²⁹
6. Final evaluable sample size (11 patients at each of 30 practices) is inflated by 30% to 15 patients at each of 30 practices (450 patients) to allow for missing primary endpoint data. Note, for the secondary endpoint of surgical complications, we anticipate a larger sample size (since all eligible patients without the individual consent will also be included) and much lower rate of missing data as these data are systematically captured in the medical record and can be extracted for most if not all patients. To ensure that the final sample size of 450 patients is met, we will allow high enrolling sites to enroll up to 25 patients (i.e., we will allow unequal enrollment across sites). Enrollment will be closely monitored centrally and intentionally controlled to achieve as much balance across sites as possible. Under the assumption that 3 sites enroll 25 patients (19 evaluable), 3 sites enroll 5 patients (3 evaluable), and all other sites enroll 15 patients (11 evaluable; equally distributed across arms), power is minimally impacted (variance inflation factor changes from 1.05 to 1.056 which has a negligible impact on power). Even under the maximal coefficient of variation of cluster sizes when cluster size is constrained at 25 and total sample size is constrained at 450, power remains at 90%.

This evaluable sample size also provides 85% power to detect the 60% versus 80% OPTI-Surg screening rates between the no-coach and coach arms with a two-sided alpha of 0.05 using a generalized linear mixed model (with logit link function) with a random practice effect to account for clustering within practice. Power estimation is based on simulation in R.

While it is possible that the effect size observed in prior studies that included younger patients undergoing less risky surgery may be larger than in older patients undergoing higher risk procedures, it is also plausible that an individualized program that targets multiple domains of frailty may result in substantial improvements in functional recovery – even among the very frail. Studies examining trajectories of functional recovery without prehabilitation, however, show that both community dwelling older adults and frail older nursing home residents, on average, achieve maximum functional recovery at 90 days after abdominal surgery. Based on this evidence, we expect that the benefits of targeted optimization of frailty traits will result in accelerated recovery across the spectrum of frailty and multi-comorbidity.¹⁸ To address this uncertainty, we will conduct an interim analysis as described in Section 9.1. Further, our target power of 90% for an effect size based on Li et al. (2013)²⁷ maintains reasonable power (i.e., power $\geq 70\%$) for slightly smaller effect sizes in the event that the effect is not as robust in the present patient population. Specifically, our sample size ensures 90% power to detect the standardized effect size of 0.42 based on Li et al. (2013), and has power of 80% and 70% power for effect sizes of 0.36 and 0.33, respectively.

12.4 Analysis plan

12.4.1 To assess the balance in randomization, baseline characteristics captured at the patient-level including age, gender, race, ethnicity, disease type, comorbidities, CHAMPS, EQ-5D-5L index and EQ-5D-5L visual analog scale will be compared across randomization arms using a generalized linear mixed model using the appropriate link function based on the distribution of the variable with a random practice effect to account for clustering within practice. Given the small number of sites, comparison of practice characteristics (e.g., practice volume; payer mix; solo, single specialty, or multi-specialty group practice; availability of geriatric specialists, palliative care providers, advanced practice providers,

patient navigators, on site occupational and physical therapy, social workers, pharmacists, dietetics, integrative medicine) across randomization arms will be descriptive.

12.4.2 Primary analysis

The primary analysis will employ a generalized linear mixed model (with Gaussian link function) with a random practice effect to account for clustering within practice and baseline CHAMPS as a covariate to compare 8-week CHAMPS between the combined OPTI-Surg no-coach and coach arms versus usual care. This analysis will include all eligible elderly patients who undergo major cancer surgery, consent to complete CHAMPS questionnaires, and have baseline and 8-week function measured. In supplemental analysis, we will compare pairwise between arms (coach vs usual care, no-coach vs usual care, and coach vs no-coach) using the same method. Supplemental analyses will include model-based analysis with covariates from patient and practice characteristics which appear to differ among randomization arms.

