Study population: The target of intervention will be surgical practices. The study will include evaluation of patients, providers, and practice organizational and structural factors. Practices will be randomized to utilize the OPTI-Surg package intervention alone, OPTI-Surg with an implementation coach, or usual care. Eligible practices will be engaged in elective cancer operations that are high risk in older adults. Based on administrative data on operative mortality, the following have been identified as high risk in older adults: Gastrectomy 3-10%; colectomy 1-2%; proctectomy 2%; esophagectomy 6-16%; pancreatectomy 2-10%; hepatectomy 3-7%; nephrectomy 2%; total cystectomy 3%; and lung lobectomy/pneumonectomy 3-9%.¹⁹ Eligible practices will have a high prevalence of patients among whom there is a high risk of frailty and be categorized as either a thoracic, major abdominal, or urologic practice. Prior research has shown that > 50% of patients aged 70+ presenting for major surgery are frail.⁶ Based on this data, patients included in the study will be (a) age \geq 70 years who are presenting for surgical evaluation for (b) one of the noted high risk procedures (listed above). To address the variation in expected functional recovery by procedure type, we plan to stratify randomization by three practice types: (1) thoracic, (2) major abdominal, and (3) urologic. Esophagogastric procedures may be included in either the thoracic or major abdominal surgery categories, depending upon the specialty of the operating surgeon.

Endpoints: This study will incorporate both patient-level and site-level data collection. For patient-level data collection, individual eligible patients will be approached for participation and

will sign a consent form for completion of questionnaires preoperatively—at baseline prior to surgery or optimization intervention—and at 8 weeks after surgery.

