7.4 Randomization

Randomization will be stratified by practice type (thoracic, major abdominal, and urologic). Pocock-Simon dynamic allocation with a 5% level of randomness (to ensure that the algorithm is not deterministic) added to the algorithm such that practices will be assigned to the arm in a 1:1:1 fashion that leads to more imbalance 5% of the time. Site randomization will be centrally performed by the Alliance Statistical and Data Center once an institution is interested and eligible to participate (see Section 4.3).

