12.4.3 Secondary and exploratory analysis

A generalized linear mixed model (with logit link function) with a random practice effect to account for clustering within practice will be used to compare postoperative complications within 12 weeks of surgery between the combined OPTI-Surg no-coach and coach arms versus usual care followed by pairwise comparisons. This analysis will also include all eligible elderly patients who undergo major cancer surgery (no documentation of postoperative complications will be considered as not having any postoperative complications). A generalized linear mixed model (with logit link function) with a random practice effect to account for clustering within practice will also be used to compare compliance rate for screening between the no-coach and coach arms. This analysis will include all eligible elderly patients with planned major cancer surgery. Generalized linear mixed models (with appropriate link function based on the distribution of the outcome variable being compared) with a random practice effect to account for clustering within practice will be used to compare other surgical outcomes within 12 weeks of surgery and to compare EQ-5D-5L index and visual analog scale scores between the combined OPTI-Surg no-coach and coach arms versus usual care. Models for EQ-5D-5L scores will include the respective baseline EQ-5D-5L score as a covariate. In supplemental analysis, we will compare outcomes and EQ-5D-5L index and visual analog scale scores pairwise between arms (coach vs usual care, no-coach vs usual care, and coach vs no-coach) using the same method. Supplemental analysis will also incorporate patient and practice characteristics which appear to differ among randomization arms.

A variety of supplemental and exploratory analyses will be conducted primarily using descriptive analysis as well as model-based analysis (where applicable and supported by adequate sample size) including to describe the frequency of interventions implemented and to explore the relationship between site characteristics and likelihood of compliance.

With the addition of the virtual EFS effective with Update #03 to the study, we will additionally explore whether outcomes differed according to EFS used (in-person vs. virtual).

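### The primary model leaves out practice type, the only factor on which the randomisation is stratified; if types differ, the standard error of the arm contrast is too large

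*Combined protocol and SAP*

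**What the plan says.** Section 7.4 states: "Randomization will be stratified by practice type (thoracic, major abdominal, and urologic"), using Pocock-Simon allocation with 5% randomness. Sections 4.3.2 and 4.6 name the same single factor. Section 1.5 gives the reason: "To address the variation in expected functional recovery by procedure type, we plan to stratify randomization by three practice types".

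Section 12.4.2 sets out the primary analysis: a Gaussian mixed model for 8-week CHAMPS comparing the two OPTI-Surg arms combined with usual care, "with a random practice effect to account for clustering within practice and baseline CHAMPS as a covariate". Practice type is not in it, and the model described for the power calculation in Section 12.3 does not have it either. Supplemental models may add "covariates from patient and practice characteristics which appear to differ among randomization arms".

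The logit model in Section 12.4.3, "with a random practice effect to account for clustering within practice will be used to compare postoperative complications within 12 weeks of surgery", has no practice-type term either.

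On between-practice variation, Section 12.3 gives one figure: "Cluster effect will be 0.005".

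**The concern.** The design treats practice type as prognostic for functional recovery, and the primary endpoint measures functional recovery. Yet the primary model does not use the factor.

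Stratified allocation spreads the three types almost evenly over the arms, so a difference between types largely cancels out of the arm contrast. A model without a type term cannot see this. It attributes the type differences to the random practice effect and reports a standard error above the true sampling error. Baseline CHAMPS removes only the part of a type difference that exists before surgery; Section 1.5 is concerned with recovery after different operations.

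The supplemental rule does not fill the gap. It is triggered by apparent imbalance between arms, which a factor balanced by design will rarely show, and a supplemental model does not change the primary result. What is at stake is the width of the primary interval and the power of a trial with only 30 practices.

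**Working it through.** **Inputs from Section 12.3.** The sample size "is based on achieving 90% power with a two sided alpha of 0.05". SD 18.3 kcal; means 19.73 and 12.10, difference 7.63 kcal; intracluster correlation (ICC) 0.005; 30 practices with 11 evaluable patients each. Allocation is 1:1:1, so the primary contrast is 20 practices against 10.

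**The plan's own figures.**
- Variance inflation is 1 + (11 − 1) × 0.005 = 1.05, as in Section 12.3 ("variance inflation factor changes from 1.05 to 1.056").
- A two-sample normal calculation with 110/1.05 and 220/1.05 patients gives 93.9% power at a standardised effect of 0.42. Adding the Section 12.1 futility look (two-sided p ≥ 0.323 at half information) gives 89.9%, and 79.6% at 0.36, against the stated 90% and 80%. The plan's power is reproduced.

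**Variance of a practice mean.**
- Between practices: 0.005 × 18.3² = 1.67.
- Within practices: 0.995 × 18.3²/11 = 30.29.
- Total 31.96; between-practice share 1.67/31.96 = 5.2%.
- Standard error of the contrast: √(31.96 × (1/10 + 1/20)) = 2.19 kcal.

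**Case A: the ICC of 0.005 already contains the type differences.** With type means at −g, 0, +g and ten practices per type, the between-type variance is (2/3)g². Setting this to 1.67 gives g ≈ 1.6 kcal. Omitting type can then widen the interval by at most √(31.96/30.29) = 1.027, or 2.7%. In simulation the standard errors are 2.28 and 2.26, about 1% apart, and power differs by about one point or less.

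**Case B: type differences come on top of the ICC (assumed).** Without a type term, the residual variance of practice means rises by about 30 × (2/3)g²/28. At g = 4 this is 11.43, so the reported standard error is about √((31.96 + 11.43) × 0.15) = 2.55.

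The simulation used Pocock-Simon allocation on type with 5% randomness, a practice-level regression with 28 or 26 degrees of freedom, practice variance floored at zero, ten practices per type, no baseline adjustment, no futility look, and 20,000 replicates per setting. The true-SD column comes from a separate run of 12,000 trials per setting.

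| Type means | Reported SE without type | True SD of that estimate | SE with type | Power without / with | Type I error without |
|---|---|---|---|---|---|
| ±2 kcal | 2.33 | 2.19 | 2.29 | 90% / 90% | 3.4% |
| ±4 kcal | 2.55 | 2.25 | 2.29 | 85% / 90% | 2.4% |
| ±6 kcal | 2.92 | 2.25 | 2.29 | 75% / 90% | 1.3% |

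With type in the model, type I error is about 3.5%. It is below 5% because the practice variance is floored at zero. If types do not differ, adjusting widens the interval by about 1%, and power is 90.3% with the term against 90.7% without.

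**Overall ICC implied by Case B:** (1.67 + (2/3)g²)/(18.3² + (2/3)g²) gives 0.013, 0.036 and 0.072 at g = 2, 4 and 6.

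**Sensitivity, at ±2, ±4 and ±6 kcal.**
- Uneven 6/18/6 mix of types: SE 2.31, 2.43, 2.66 without type against 2.28 with it; power 90%, 88%, 83% against about 91%.
- Baseline CHAMPS explaining 25% of within-practice variance (assumed), 10/10/10 mix: SE 2.05, 2.31, 2.72 against 1.99; power 96%, 92%, 83% against 96%.

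**The case against.** The strongest reply is that this hardly matters on the plan's own inputs. The only documented figure for between-practice variation is an ICC of 0.005. Under it the interval changes by about 1%, roughly what the extra term costs if types do not differ.

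Material loss needs spreads the documents do not give. At ±2 kcal there is essentially none. At ±4 and ±6 kcal the implied ICCs are about 7 and 14 times the planned value, and the type means span 8 and 12 kcal, both more than the planned effect of 7.63. The 85% and 75% figures also leave out the baseline covariate that the plan includes. With a baseline explaining 25% of within-practice variance, power stays above 90% at ±4 kcal. Nothing was calculated for the logit complication model, where adding a covariate also changes the conditional odds ratio being estimated.

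All of this stands, and it limits the size of the point. It does not remove it. Section 1.5 itself expects recovery to vary by procedure type, the omission can only lose precision, and the supplemental rule is poorly suited to restoring a balanced factor. For complications the case is consistency with the randomisation, not a computed gain.

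**Conclusion.** The concern holds. The primary model omits the one factor the trial stratifies on, and where practice types differ after baseline adjustment the reported standard error of the arm contrast exceeds its true sampling error. This affects efficiency, not validity: the estimate is not biased, false positives are not inflated, and the stated 90% power stands on its own assumptions.

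The loss is about 1% in interval width (2.7% at most) if the ICC of 0.005 already covers type differences. It becomes material at around ±4 kcal on top of that ICC, where the standard error is 2.55/2.29 = 1.11 times as large and power is about five points lower before any baseline adjustment. The ±6 kcal result is an extreme. These figures assume equal cluster sizes, SD 18.3 kcal, ten practices per type and no futility look. The change should be made because its cost is close to nil whichever case applies.

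**What to change.** In Section 12.4.2, add practice type (thoracic, major abdominal, urologic) as a pre-specified three-level fixed effect in the primary CHAMPS model, alongside arm, baseline CHAMPS and the random practice effect. Add the same term to the complication model in Section 12.4.3 so that the analysis follows the randomisation. For the penetration model, with about 20 practices in two arms, the term is optional.

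This is a wording change only. Practice type is known for every practice at randomisation, so no new data are needed. The statistical cost is two between-practice degrees of freedom. Fixing the term now also avoids choosing the model after results are seen.

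### The primary analysis leaves out patients with an observed 8-week CHAMPS score when baseline CHAMPS is missing, and sections 12.4.2 and 12.4.4 need reconciling on this

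*Combined protocol and SAP*

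**What the plan says.** Section 12.2.1 defines the primary endpoint as "CHAMPS total score 8 weeks after surgery", which is a level and not a change from baseline. Section 12.4.2 fits a Gaussian mixed model with a random practice effect and "baseline CHAMPS as a covariate to compare 8-week CHAMPS" between the combined OPTI-Surg arms and usual care. It restricts that analysis to eligible patients who have major cancer surgery, "consent to complete CHAMPS questionnaires, and have baseline and 8-week function measured".

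Section 12.4.4 handles missing data in three ways:
- It compares baseline characteristics of patients with and without an 8-week score.
- It says the initial analysis will use every available observation, followed by propensity-weighted regression as a supplement if systematic differences are seen.
- It adds single and multiple imputation, with results compared descriptively. It does not say how a missing baseline CHAMPS is treated.

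Section 12.3, assumption 6, goes from 330 evaluable patients (11 at each of 30 practices) to 450 (15 at each) "to allow for missing primary endpoint data".

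**The concern.** Baseline CHAMPS is in the model for precision. Requiring it for entry to the analysis set means that a patient who had surgery and returned the 8-week questionnaire contributes nothing to the primary comparison if the baseline form is absent. That discards the outcome the trial was set up to collect.

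The two analysis sections also leave the rule unclear. If the initial analysis in section 12.4.4 means all complete pairs, it agrees with section 12.4.2. If it means all observed 8-week scores, the primary populations differ. The choice should be settled before the data are seen. Imputation does not settle it, because as written it is a descriptive comparison that leaves the section 12.4.2 set unchanged.

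At stake are some precision and an unambiguous primary population.

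**Working it through.** **Inputs from section 12.3.** Power and alpha: "achieving 90% power with a two sided alpha of 0.05 using a generalized linear mixed model". Effect: the combined OPTI-Surg arms against usual care "is a mean score (kcal) of 19.73 versus 12.10 at 8 weeks post-surgery". Spread: "Standard deviation of the CHAMPS score (kcal) is 18.3". The intracluster correlation is 0.005, with 330 evaluable patients in 30 practices. Section 12.1 gives 1:1:1 allocation, hence 10 usual-care practices against 20, and a non-binding futility look at half the patients with a cut-off of p ≥ 0.323.

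**Inputs not in the documents (assumptions).** The share f of 8-week completers without a baseline: 3%, 5% or 10%. The baseline-to-8-week correlation r: 0 in the main calculation, then 0.2 to 0.4.

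**Step 1: reproduce the plan's effect size.**
- Usual care: 0.59×8 + 0.41×18 = 12.10.
- OPTI-Surg, with average screening (60% + 80%)/2 = 70%: frail 0.7×23 + 0.3×8 = 18.5; non-frail 0.7×23 + 0.3×18 = 21.5; overall 0.59×18.5 + 0.41×21.5 = 19.73.
- d = (19.73 − 12.10)/18.3 = 7.63/18.3 = 0.417, which the plan rounds to 0.42.

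**Step 2: reproduce the plan's power.** The design effect is DE = 1 + (N/30 − 1)×0.005. With a 1:2 split the expected test statistic is θ = d × √(N × (1/3) × (2/3) / DE).
- At N = 330, DE = 1.05 and θ = 0.417 × √(73.33/1.05) = 3.48.
- Fixed-design power is Φ(θ − 1.96) = 93.6% (93.9% at d = 0.42).
- With the look, power is P(Z₁ > 0.988 and Z₂ > 1.96). Here Z₁ has mean θ/√2, Z₂ has mean θ, their correlation is √0.5, and 0.988 is the normal value for a two-sided p of 0.323. This gives 89.5% (89.9% at d = 0.42). The stated 90% therefore reproduces when the futility rule is read as two-sided and always followed.

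**Step 3: drop patients without a baseline.** N = 330 × (1 − f), no credit for baseline adjustment (r = 0), d = 0.417:

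| f | N | DE | θ | Power, futility rule followed | Power, no look |
|---|---|---|---|---|---|
| 0 | 330 | 1.050 | 3.48 | 89.5% | 93.6% |
| 3% | 320 | 1.048 | 3.43 | 88.7% | 93.0% |
| 5% | 314 | 1.047 | 3.40 | 88.1% | 92.6% |
| 10% | 297 | 1.045 | 3.31 | 86.5% | 91.2% |

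The losses with the rule followed are 0.8, 1.4 and 3.0 points. Keeping all 330 patients returns the first row.

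**Step 4: credit baseline adjustment.** Scaling the residual variance by 1 − r² (θ divided by √(1 − r²)), with the futility rule followed:
- r = 0.2: 89.3% at 5% loss.
- r = 0.3: 91.9% with no loss, 90.8% at 5%, 89.3% at 10%.
- r = 0.4: 91.4% at 10% loss.

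**Step 5: does filling in recover the precision?** A simulation used 330 patients, 30 practices, ICC 0.005, true effect 0.42, baseline missing completely at random and overall-mean fill-in without an indicator. Both approaches were unbiased (mean estimates 0.417 to 0.423). At 10% missing, the standard error was 0.119 with fill-in against 0.126 with dropping (r = 0), and 0.109 against 0.113 (r = 0.5). The gain shrinks as r rises, because filled-in patients are adjusted less. Missingness that differs by arm was not simulated.

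**The case against.** **The group may be small.** Baseline follows consent, before or after registration, and may be obtained by email, mail, telephone or telehealth (sections 5.1 and 8.4.1). Section 12.4.4 adds central completeness monitoring and monthly site contact. No rate is given. This stands, and it keeps the point minor.

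**Power below 90%.** A reader might infer that power falls below the planned figure. The documents do not show this. The values under 90% in step 3 assume that the non-binding futility rule is always followed and that baseline adjustment buys nothing. Without the look, power is 91.2% even at 10% loss. With the rule followed, r = 0.3 leaves 90.8% at 5% loss.

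**Losses beyond the allowance.** A reader might infer that these exclusions come on top of the inflation to 450, since that is described as covering missing endpoint data. The wording leans that way but does not settle it. Evaluable may mean belonging to the section 12.4.2 set, in which case missing baselines are already inside the allowance.

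**Late baselines.** A reader might also infer that late baseline forms are set aside, which would enlarge the group. Nothing in the documents says so, and section 5.1 allows completion at any time after consent.

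**Imputation is planned.** Nothing confines it to the 8-week score, so it could cover baseline. That softens the point, but it leaves the primary set as it is and does not resolve the two sections.

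**The remedy has a weakness.** Practices are randomized before patients consent, so recruitment and baseline completion could differ by arm. Filled-in patients would then be less fully adjusted. This also stands, and it is why the both-measured analysis should be kept.

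**Conclusion.** The point holds as an efficiency and clarity issue. Section 12.4.2 excludes patients with an observed primary endpoint because a covariate is missing, and section 12.4.4 is worded in a way that does not sit comfortably with that rule. If 3% to 10% of 8-week completers lack a baseline, 10 to 33 of 330 patients are lost. The cost is about 0.8 to 3.0 power points with the futility rule followed, or 0.6 to 2.4 points without the look (93.6% to between 93.0% and 91.2%).

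These sizes rest on an assumed missing-baseline share, d = 0.417, ICC 0.005 and no credit for baseline adjustment. They show a modest loss of precision. They do not establish a shortfall against 90%, a loss beyond the allowance for missing data, or any exclusion of late baselines.

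**What to change.** In section 12.4.2:
- Define the primary set as eligible, consented patients who had surgery and have an 8-week CHAMPS score.
- Fill a missing baseline CHAMPS with the overall baseline mean across arms, using neither arm nor outcome, and add a missing-baseline indicator to the model.
- Report the number of missing baselines by arm.
- Keep the both-measured analysis as a sensitivity analysis. If its result differs materially and baseline completion is uneven between arms, interpret the primary result with that in mind.

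In section 12.4.4, reword the initial-analysis sentence so that it names the same set.

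The cost is a few sentences, with no added data, visits or patients. The downside is less complete adjustment for filled-in patients if baseline completion differs by arm, which the sensitivity analysis would check.
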